**\*\*\* Subject Population \*\*\***

**Subject Population(s) Checklist**

**Select All That Apply :**

- X Adults  
 Cognitively Impaired Subjects  
 Employees (specifically targeted)  
 Fetuses  
 Minors (under 18)
- X Pregnant Women  
 Prisoners  
 Students (specifically targeted)  
 Terminally Ill Subjects  
 Wards of the State  
 Other (e.g., non-English speaking or any population that is not specified above)

---

**\*\*\* Expedited Paragraphs \*\*\***

To request an Expedited Review, check the appropriate category(ies) below. Provide justification for your request for Expedited Review.

To qualify for expedited review, research activities must (1) present no more than minimal risk to human subjects, and (2) involve only procedures listed in one or more of the categories below.

1. Clinical studies of drugs and medical devices only when condition (a) or (b) is met.
  - a) Research on drugs for which an investigational new drug application (21 CFR Part 31, 32) is not required. (Note: Research on marketed drugs that significantly increases the risks or decreases the acceptability of the risks associated with the use of the product is not eligible for expedited review.)
  - b) Research on medical devices for which
    - (i) An investigational device exemption application (21 CFR Part 812) is not required; or
    - (ii) The medical device is cleared/approved for marketing and the medical device is being used in

**Protocol Title:** Smoking Cessation Following Text Message Intervention in Pregnant Women

---

accordance with its cleared/approved labeling.

2. Collection of blood samples by finger stick, heel stick, ear stick, or venipuncture as follows:
  - a) From healthy, nonpregnant adults who weigh at least 110 pounds. For these subjects, the amounts drawn may not exceed 550 ml in an 8-week period and collection may not occur more frequently than 2 times per week; or

From other adults and children, considering the age, weight, and health of the subjects, the collection procedure, the amount of blood to be collected, and the frequency with which it will be collected. For these subjects, the amount drawn may not exceed the lesser of 50 ml or 3 ml per kg in an 8-week period and collection may not occur more frequently than 2 times per week.

Children are "persons who have not attained the legal age for consent to treatments or procedures involved in the research, under the applicable law of the jurisdiction in which the research will be conducted."

3. Prospective collection of biological specimens for research purposes by non-invasive means.

**EXAMPLES:** (a) hair and nail clippings in a nondisfiguring manner; (b) deciduous teeth at time of exfoliation or if routine patient care indicates a need for extraction; (c) permanent teeth if routine patient care indicates a need for extraction; (d) excreta and external secretions (including sweat); (e) uncannulated saliva collected either in an unstimulated fashion or stimulated by chewing gumbase or wax or by applying a dilute citric solution to the tongue; (f) placenta removed at delivery; (g) amniotic fluid obtained at the time of rupture of the membrane prior to or during labor; (h) supra- and subgingival dental plaque and calculus, provided the collection procedure is not more invasive than routine prophylactic scaling of the teeth and the process is accomplished in accordance with accepted prophylactic techniques; (i) mucosal and skin cells collected by buccal scraping or swab, skin swab, or mouth washings; (j) sputum collected after saline mist nebulization.

4. Collection of data through non-invasive procedures (not involving general anesthesia or sedation) routinely employed in clinical practice, excluding procedures involving X-rays or microwaves. Where medical devices are employed, they must be cleared/approved for marketing. (Studies intended to evaluate the safety and effectiveness of the medical device are not generally eligible for expedited review, including studies of cleared medical devices for new indications.)

**EXAMPLES:** (a) physical sensors that are applied either to the surface of the body or at a distance and do not involve input of significant amounts of energy into the subject or an invasion of the subjects' privacy; (b) weighing or testing sensory acuity; (c) magnetic resonance imaging; (d) electrocardiography, electroencephalography, thermography, detection of naturally occurring radioactivity, electroretinography, ultrasound, diagnostic infrared imaging, doppler blood flow, and echocardiology; (e) moderate exercise, muscular strength testing, body composition assessment, and flexibility testing where appropriate given the age, weight and health of the individual.

5. Research involving materials (data, documents, records, or specimens) that have been collected, or will be collected solely for nonresearch purposes (such as medical treatment or diagnosis). (NOTE: Some research in this category may be exempt from the HHS regulations for the protection of human subjects. 45CFR 46.101(b)(4). This listing refers only to research that is not exempt.)

**Protocol Title:** Smoking Cessation Following Text Message Intervention in Pregnant Women

---

6. Collection of data from voice, video, digital, or image recordings made for research purposes.
7. Research on individual or group characteristics or behavior (including, but not limited to, research on perception, cognition, motivation, identity, language, communication, cultural beliefs or practices, and social behavior) or research employing survey, interview, oral history, focus group, program evaluation, human factors evaluation, or quality assurance methodologies. (NOTE: Some research in this category may be exempt from the HHS regulations for the protection of human subjects. 45 CFR 46.101(b)(2) and (b)(3). This listing refers only to research that is not exempt.)
- X 8. [FOR IRB use only]. Continuing review of research previously approved by a convened IRB only when condition (a), (b), or (c) is met.
- a) Previously approved research where
- (i) The research is permanently closed to the enrollment of new subjects;
- (ii) All subjects have completed all research-related interventions; and
- (iii) The research remains active only for the long term follow-up of subjects.
- b) Previously approved research where no subjects have been enrolled and no additional risks have been identified.
- X c) Previously approved research where the remaining research activities are limited to data analysis.
9. [FOR IRB use only]. Continuing review or research not conducted under an investigational new drug application or investigational drug exemption where expedited categories two (2) through eight (8) do not apply but the IRB has determined and documented at a convened meeting that the research involves no greater than minimal risk and no additional risks have been identified.

---

**\*\*\* Background, Purpose, Study Procedures \*\*\***

**Title**

Smoking Cessation Following Text Message Intervention in Pregnant Women
---

**Complete Sections 1 - 16. In sections that allow reference to sponsor protocol or grant, clearly state section and page numbers. Any information that is different or specific to the local site should be in the SLU application. Specify N/A as appropriate. Do not leave any required sections blank.**

**1. Background**

Page numbers from a sponsor's protocol/grant may be referenced in 1a and 1b.

- a) Provide an introduction and background information. Describe past experimental and/or clinical findings leading to the formulation of the study, if applicable. Investigator Initiated studies must cite references in the response provided or attach a bibliography. \* ?HELP?\***

Smoking during pregnancy has been shown to have detrimental effects on both the mother and the fetus. The perinatal period presents a critical opportunity to educate and support the mother as she attempts quit. Current studies suggest a median quit rate of only 4.9% in women receiving usual care (Cognitive Behavioral Therapy, CBT), but a number of studies have investigated new interventions in addition to usual care to help increase compliance with smoking cessation. Pharmacological aids such as nicotine replacement therapy (NRT) and bupropion are recommended as potential options by the American College of Obstetrics and Gynecology since they are considered safer than continued smoking during pregnancy. Studies thus far on smoking cessation with the help of electronic devices have demonstrated mixed results; however, the impact of texting in the pregnant population in combination with CBT and pharmacological therapy has yet to be assessed.

Smoking during pregnancy has been shown to have detrimental effects on both the mother and the fetus. Cigarettes contain over 3000 compounds many of which can cause risk to pregnancy. However, the nicotine and carbon monoxide components are of primary concern.1-8 Nicotine releases epinephrine, which results in a decrease in uterine blood flow and an increase in uterine resistance. There is also decreased production of fetal nitric oxide resulting in lower blood flow to the fetus and leading to decreased birth weight, length, and head circumference compared to non-smokers.9

Studies have proven that exposure to tobacco can increase the risk for placental abruption, placental previa, preterm birth, antenatal death, sudden infant death syndromes, attention-deficit/hyperactivity disorder and asthma.2-8 Compared to children of non-smoking mothers, children of mothers who smoked during pregnancy had a higher BMI and increased odds for being overweight at 4-years of age; however, in the children whose mother quit smoking during pregnancy there was no increased risk of increased BMI or being overweight compared to the children of non-smoking mothers.10 According to the data from the 2009 Pregnancy Risk Assessment and Monitoring System (PRAMS) approximately 12.4% of pregnant women with live births reported smoking during the last three months of pregnancy (PRAMS).11 Of the 25% of women who smoked in the 3 months prior to pregnancy, 52% quit during pregnancy; of those, 44% relapsed within 6 months after delivery. The perinatal period presents a critical opportunity to educate and support the mother as she attempts quit.

Current studies evaluating rates of smoking cessation in pregnant women show less than ideal results. A primary analysis of 12 pooled trials found a median quit rate of 4.9% in women with usual care. This rate increased to 13.2% in patients that received tailored self-help intervention.12 To help increase compliance with cessation, studies have investigated new interventions as part of the usual care provided to pregnant patients that continue to smoke. One study looked at including a 15-minute video and provider prompting at baseline and one month. Although a higher percentage of patients in the intervention group had a higher 30-day abstinence rate at 2-months post baseline, the finding was not significant (26.1% vs 10.5%, p=0.12) although the study did not discuss if this was an appropriately powered sample size.13 Another study looking at the combination of smoking cessation education, physical activity counseling and supervised exercise found a 25% abstinence rate at 8-months gestation.14 The use of NRT has also been studied. One study found that CBT plus NRT verses CBT alone was effective at 7-weeks (24% vs 8%, p=0.02) and 38-weeks' gestation (18% vs 7%, p=0.04), unfortunately there was no benefit at 3-months post-partum (20% vs. 14%, p=0.55).15

The use of pharmacological aids for smoking cessation is recommended as a potential option

**Protocol Title:** Smoking Cessation Following Text Message Intervention in Pregnant Women

---

by the American College of Obstetrics and Gynecology. Currently, NRT products and bupropion are appropriate options during pregnancy and are the most utilized therapy for cessation during pregnancy. Although classified as pregnancy category-D medication, NRT patches are often used to assist the pregnant patient in smoking cessation when CBT is not successful. A review looking at 4-studies that examined pregnancy outcomes after NRT, found a significant decrease in the risk of preterm delivery and low-birth weight compared to active smokers. NRT is considered safer than continued smoking since it only provides nicotine whereas smoking provides nicotine plus over 3000 other chemicals. It has also improved cessation rates near the quit date compared to CBT in obstetric patients. Similarly, bupropion has improved cessation rates in non-obstetric patients and has not been associated with malformations or abnormal pregnancy outcomes.

The transtheoretical stages of change assessment is beneficial to help determine a patient's readiness to quit. Data has shown that the stages predict preparation for cessation and successful cessation. In the precontemplative stage, patients are not willing to consider smoking cessation. The contemplative stage is defined as patients considering smoking cessation but not ready to set a quit date. Preparation stage occurs when patient is ready to set a quit date within the next 30 days. In the action stage, patients have been smoke free for less than six months. Maintenance stage is cessation longer than 6 months. Relapse is when patients have starting smoking again after being in the action stage. In other obstetric smoking cessation literature, relapse has been defined as smoking more than 5 cigarettes or smoking more than 5 times since cessation.

Mobile technology is common place in today's society. According to the 2013 Nielsen report, 94% of all Americans 16 years of age or older use a cellular phone with more than half of those being smart phones. A total of 96% of phone owners have a data plan included. In 2012, the average monthly usage included 164.5 calls, 644.1 voice minutes, and 764.2 text messages. Ownership of cell phones and high tech devices extends to all socioeconomic classes, and the ease and affordability has made cell phone use common for all races and income brackets. When looking at text message specifically for race 79% of whites, 85% of Blacks and 87% of Hispanics report text messaging. When looking at household income 78% of those making < 30K, 80% of those making between 30k-50k, and 88% of those making greater than 50k are active texters. African Americans are more likely than the general population to own smart phones (71% vs. 62%) and are 44% more likely than the broader market to create a social media profile. Over a monthly basis, African Americans also spend 24% more time on their phone, 12% more time on email, and 10% more time on the internet. Hispanics text the greatest of all ethnic groups at 943 text messages per month. Based on this data, it is apparent that mobile phone messaging is a potential convenient and cost-effective way to interact with patients of all races and income levels.

Results of current studies looking at smoking cessation with the help of computer or other electronic device are mixed. Several trials have looked at the use of text-messaging based smoking cessation programs. One randomized controlled pilot trial of 151 daily smokers interested in quitting found a non-clinically significant difference in cessation rates at 3 months between the intervention and control groups (11% versus 4%), this study was not powered to detect a statistical difference. A small pilot study evaluating Text2Quit, an automated, personalized, and interactive program that sends texts and emails over the course of 3 months, reported liking the program at 2 and 4 weeks after enrollment (91% and 82%, respectively) and 75% of participants reported reading most or all of the messages sent. Unfortunately, the majority of participants admitted to smoking at the 4-week visit. The txt2stop study was a trial of 5800 smokers that were randomized to receive text messages that were comprised of motivational and behaviour-change support versus the control group who received text messages unrelated to quitting. At 6-months abstinence was significantly increased in the intervention group versus the control group (10.7% vs. 4.9%;  $p < 0.0001$ ).

**Please save frequently**

**Protocol Title:** Smoking Cessation Following Text Message Intervention in Pregnant Women

---

- b) Describe any animal experimentation and findings leading to the formulation of the study, if there is no supporting human data.

N/A

## 2. Purpose of the study

- a) Provide a brief lay summary of the project in <200 words. The lay summary should be readily understandable to the general public.

We propose an 18-month, randomized, open-label evaluation of the impact of texting to pregnant, underserved, cigarette smokers on smoking cessation rates. Patients will be eligible if they have a confirmed pregnancy, obstetric care provided at the St. Mary's Health Center Maternal Fetal Care Center, are English speaking, at least 18 years of age, are in the preparation stage of change and willing to set a quit date within 30 days and before 35 weeks gestation, and have a cellular phone that is capable of receiving text messages. Patients will be randomized to either the texting group or control group. A baseline carbon monoxide level will be obtained. The patient, regardless of group, will have the standard of care smoking cessation visit. If the pharmacist, physician, and patient deem that pharmacotherapy is appropriate, they will receive nicotine replacement therapy patches or bupropion free of charge in 2-week intervals. Patients in the intervention group will receive text messages focused on smoking cessation and pregnancy. Patients will be seen on a bi-weekly schedule to obtain additional vouchers for patches or for bupropion, meet with the pharmacist, and complete a carbon monoxide exhalation test. These visits will be continued until the pharmacotherapy course is complete. Patient information on additional barriers to stop smoking will also be obtained including the ongoing use of marijuana and alcohol. This information is also collected as standard of care for all pregnant women seen by our group.

Page numbers from a sponsor's protocol/grant may be referenced in 2b and 2c.

- b) List your research objectives (specific aims & hypotheses of the study).

The primary objective of the study is to evaluate the impact of a text-message service on smoking cessation in medically underserved, obstetric patients when added to the usual care of pharmacist-driven CBT smoking cessation program and smoking cessation pharmacotherapy with either the nicotine replacement patch or bupropion. The smoking cessation rate will be verified by exhaled carbon monoxide levels (<8ppm) at 2 weeks of the patients quit date. Secondary objectives of the study include (1) a comparison of self-reported cessation versus verified cessation from the exhaled carbon monoxide level, (2) self-reported cessation rates at 1 month, 3 months, and delivery as verified by exhaled carbon monoxide levels, and (3) change in exhaled carbon monoxide levels from baseline to 2 week follow-up, (4), to better understand which patients may face additional barriers with tobacco cessation during pregnancy and ongoing use of marijuana and alcohol may be predictive.

**Please save frequently**

- c) Describe the study design (e.g., single/double blind, parallel, crossover, control, experimental, observational, etc.). If the study is investigator-initiated, a timeline for individual subject recruitment, follow-up, and analysis for the study is required. Also, indicate if the subjects will be randomized.

**Protocol Title:** Smoking Cessation Following Text Message Intervention in Pregnant Women

---

We propose an 18-month prospective, randomized, open-label evaluation of the impact of texting to pregnant, underserved, cigarette smokers on smoking cessation rates.

March 2014: Obtain IRB approval  
 April 1 2014: Begin enrolling patients via randomization  
 April 31st, 2015: Cease enrollment of new patients  
 June 1st 2015: Final collection of all data for all enrolled patients  
 Summer 2015: Data analysis, manuscript preparation

d) **If subjects will be given placebo, please justify placebo use. \*?HELP?\***

N/A

### 3. Study Procedures

- a) **N** Is this project a multicenter study (i.e., same project is conducted elsewhere by a different investigator) OR does this study involve conduct of research at multiple sites?  
 Is SLU acting as a coordinating center for other sites OR is the SLU PI a direct recipient of a federal grant for this research? If yes, complete and attach the Supplemental Application for Coordinating Center Activities.  
 Will the SLU site be participating in all parts/procedures/arms of the study?

**If No, explain what SLU will NOT participate in:**

**Please save frequently**

Page numbers from a sponsor's protocol/grant may be referenced in 3b, 3c, and 3d.

- b) **Describe all the procedures, from screening through end-of-study, that the human subject must undergo in the research project, including study visits, drug treatments, randomization and the procedures that are part of standard of care. Specify which procedures are for research and which are standard of care. Please note: The box below is for text only. If you would like to add tables, charts, etc., attach those files in the Attachment section (#16).**

This is a randomized, open-label, prospective trial that will evaluate the impact of texting to pregnant, underserved, cigarette smokers on smoking cessation rates. It will be conducted over 18-months, with subject recruitment over 12 months, at St. Mary's Health Center Maternal Fetal Care Center. Potential patients will be identified through EPIC chart review as well as from referrals from providers. These patients will be screened for inclusion and exclusion criteria through a chart review as well as meeting with pharmacy to determine the patient's stage of change and willingness to set a quit date within the next 30 days. Informed consent will be obtained if the patient is eligible and willing to participate.

As part of routine care at the Maternal Fetal Care Center, pregnant women that are active smokers are encouraged to quit. If the patient is interested in quitting smoking, the physician or pharmacist will schedule a smoking-cessation consultation visit with maternal-fetal clinical pharmacist. During this pilot study, women who have expressed interest in quitting and meet the inclusion and exclusion criteria will be approached and offered enrollment in the smoking cessation study. Patients who consent will be randomized to either the texting group or control group. For randomization purposes, an equal number of notecards will be made for the two groups. We will use a random number generator to help with patient randomization. These

**Protocol Title:** Smoking Cessation Following Text Message Intervention in Pregnant Women

---

groups. We will use a random number generator to help with patient randomization. These numbers will be placed in a sealed envelope and shuffled. At the time of patient inclusion, an envelope will be selected by the pharmacist. However, if a patient declines receiving text messages but consents to participate in the pharmacist driven CBT and NRT, she will be enrolled in the standard of care group. A baseline carbon monoxide level will be obtained.

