#### Description of Usual Care

The patient, regardless of group, will have the standard of care smoking cessation visit with the clinical pharmacy specialist or PGY2 ambulatory care resident. The visit will include

- Medication reconciliation
- Review social history which includes use of street drugs and alcohol, allergies, and vaccine history
- Obtain smoking history that included current amount smoking, changes in smoking habits during this pregnancy, number of years smoked, quit attempt history, and use of previous smoking cessation aids
- Design a quit plan that includes setting a quit date within the next 30 days, obtain follow-up contact information, identify motivators/triggers/barriers, discuss withdrawal symptoms, develop plan for management of withdrawal symptoms, develop a plan for behavior modifications, discuss rewards, handling of relapse, medication options for cessation during pregnancy, and education on purpose, proper use, potential maternal and neonatal adverse events

If the pharmacist, physician, and patient deem that pharmacotherapy is appropriate, the patient will receive a 2 week supply if using NRT or 3 week supply if using bupropion. The smoking cessation pharmacotherapy will be supplied free of charge to the consenting participants. If the patient is prescribed NRT patches, the medication will be provided in two week intervals. If the patient is prescribed bupropion, the medication will be provided for a 3 week supply with the initial dispensing and 2 week supply thereafter. Dosing and length of treatment will follow package insert approved dosing. Patients will receive a voucher to take to the Clayton Health Services Pharmacy located across the street from the Maternal Fetal Care Clinic to receive either medication at no cost.

Demographics, social history, gestation age at enrollment, estimated due date, medications at enrollment, past medical history, and obstetric history include gravity and parity will be obtained from the EPIC medical record. Patients will be asked about smoking history, time to first morning cigarette, previous quit attempts, previous experience with cessation pharmacotherapy, motivators, triggers, and barriers during initial visit.

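### Section 3b has the pharmacist select an envelope from a shuffled pile, with no opening order, log or independent custody described

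*Combined protocol and SAP*

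**What the plan says.** The whole allocation procedure is in Section 3b (Study Procedures):

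- For a two-group allocation, "an equal number of notecards will be made for the two groups". The size of the pile is not given.
- "We will use a random number generator to help with patient randomization". How the generated numbers relate to the cards is not explained.
- "These numbers will be placed in a sealed envelope and shuffled".
- "At the time of patient inclusion, an envelope will be selected by the pharmacist".

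The next sentence says that a woman who declines texts but accepts the rest of the programme is enrolled in the standard of care group. Baseline carbon monoxide (CO) is mentioned after that, without saying whether it is measured before or after the envelope is opened.

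On pharmacy's other roles, Section 3b has screening partly done by "meeting with pharmacy to determine the patient's stage of change and willingness to set a quit date within the next 30 days", and Section 8h makes the preparation stage and a quit date within 30 days conditions of entry. Under Description of Usual Care, every woman has a "standard of care smoking cessation visit with the clinical pharmacy specialist or PGY2 ambulatory care resident". The follow-up text has women meet the pharmacist and do the CO test at the same visits. The trial is open-label.

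**The concern.** Sealing hides an assignment until the envelope is opened. It does not settle which envelope belongs to which woman. When the next envelope is whichever one is selected, there is no expected assignment to compare with the one made. Someone who opened an envelope, disliked the result and drew another would break no written rule about order and would leave no required record.

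This matters more here for two reasons. Pharmacy has met the woman and judged her readiness to quit before the draw, so the people close to the envelopes have a view of her prognosis. And because the trial is open-label, concealing the assignment up to the draw is the main guard against selecting likely quitters into one arm. CO verification of the outcome does not replace that guard: if likelier quitters are placed in one arm, their verified quit rate is higher whatever the texts do.

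**Working it through.** **Step 1: what the procedure controls.** Setting the text of Section 3b against the features that make an envelope scheme checkable:

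- Random source: present (generator, shuffling).
- Assignment hidden before opening: envelopes are sealed; opacity is not mentioned.
- External numbering and fixed order: not described; shuffling followed by selection fits poorly with numbered envelopes used in sequence.
- Woman identified on the envelope before opening: not described.
- Log reconciled to a list: not described.
- Custody by someone who does not screen or treat: not described; the pharmacist selects.

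The equal-card rule gives a partial check. If the pile size were known and the remainder counted, a discarded card would show as a mismatch with enrolment. An envelope exchanged for another, or opened and put back, need not show.

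**Step 2: illustration of size.** The plan gives no figure for bias, so there is none to reproduce. From the Power Calculation paragraph in Section 3d come a 30% control quit rate, an anticipated 5-point gain and 60 patients. The prognosis split and the steered share are assumptions.

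Assume half the women have good prognosis (quit rate *h*) and half poor (*l*), averaging 30%, and no true effect of texting. A share *s* of women is steered, good to texting and poor to control; the rest split evenly. The good-prognosis fraction is then 0.5 + 0.5*s* in the texting arm and 0.5 − 0.5*s* in control, so

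false difference = [(0.5 + 0.5*s*)*h* + (0.5 − 0.5*s*)*l*] − [(0.5 − 0.5*s*)*h* + (0.5 + 0.5*s*)*l*] = *s*(*h* − *l*).

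| *h* vs *l* | *s* = 10% | *s* = 25% | *s* = 50% |
|---|---|---|---|
| 35% vs 25% | 1 point | 2.5 points | 5 points |
| 40% vs 20% | 2 points | 5 points | 10 points |
| 45% vs 15% | 3 points | 7.5 points | 15 points |

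The share needed to produce the whole anticipated effect is 0.05/(*h* − *l*): 50%, 25% and about 17% for the three rows. In 60 women, *s* = 25% means 15 steered. Half of those would have landed in the same arm anyway, so about 7 or 8 assignments would actually change. Sample size does not enter the formula, so the table is the same for the 100 subjects given in Section 8b.

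**Step 3: what better envelopes leave untouched.** Suppose a share of 60 women decline texts and go to control without a draw, with quit rates below the 30% assumed for the others (both assumed).

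- 5% decline and quit at 20%: 57 randomized, 28.5 per arm, control 31.5; control rate (28.5 × 0.30 + 3 × 0.20)/31.5 = 29.0%, a false difference of about 1 point.
- 20% decline and quit at 10%: 48 randomized, 24 per arm, control 36; control rate (24 × 0.30 + 12 × 0.10)/36 = 23.3%, a false difference of 6.7 points.

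It is zero if decliners also quit at 30%. This route needs no misuse of an envelope.

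**The case against.** The best defence is that the method is sound if followed. A shuffled pile of sealed envelopes with equal numbers per group is a valid random allocation rule, and bias arises only if someone departs from it. This is a single-site pilot with a CO-verified outcome. Participants have code numbers and a master list exists (Section 11c), so assignments are not wholly untraceable. The grant proposal and data collection sheets listed in Section 16 are not available here and may describe a log. Finally, the Expedited Paragraphs mark the remaining work as data analysis only, so a new envelope procedure may come too late to protect anyone.

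Most of this stands as a limit on the point. A reader might infer several stronger things that the documents do not support:

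- That the envelopes were unnumbered and no log was kept. The text is silent; only the absence of a description can be stated.
- That one pharmacist screens, treats and tests. The cessation visit may be given by a specialist or a resident, Section 13 has research staff obtain consent, and no operator is named for the CO test.
- That tampering would leave no trace. A counted equal-card pile could reveal a discarded card.
- That numbering alone would settle the matter. It shows out-of-order use only with a reconciled log, and it leaves the rule for women who decline texts as it is.

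What the defence does not answer is that the written procedure leaves the choice of envelope to someone in the team that judges eligibility and delivers treatment, and asks for no record of that choice.

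**Conclusion.** The point holds as a weakness in how allocation is protected, not as evidence that allocation failed. Section 3b describes random assignment but nothing that would prevent or record an exchanged envelope or a second draw, in an open-label trial where pharmacy staff both assess a subjective entry criterion and treat.

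The size of any bias cannot be estimated from the documents. The range of 1 to 15 points rests wholly on the assumed prognosis splits and steered shares. Its upper corner needs half of all women steered and a threefold difference in quit rates between prognosis groups. The useful comparison is with the 5-point effect the plan anticipates: moderate steering under a moderate split could equal it. That is enough to justify an inexpensive safeguard and no more.

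**What to change.** Replace the shuffle-and-select step in Section 3b as follows:

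- An existing team member who does not enrol women makes the allocation list with the random number generator, and prepares and holds opaque, sealed, consecutively numbered envelopes.
- The next number is opened only after consent, eligibility and baseline CO are recorded.
- The study ID and date are written on the envelope before it is opened.
- A log of every number, used or unused, is reconciled against the list.

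The cost is some preparation, a log sheet and a short rewording of Section 3b. Sample size, alpha, power and the 1:1 ratio do not change. The rule for women who decline texts needs its own remedy: analyse those women apart from the randomized comparison.

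If enrolment is already complete, the procedure can no longer be changed. In that case, reconcile the used envelopes and recorded assignments where they survive (Section 11c has paper data destroyed after entry and the master list destroyed at completion), and report the allocation method as used, as a limitation.
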